**14.2.8 Duration and type of ventilation**

This is based on CRF procedure information (PR domain). Total duration of invasive and non-invasive ventilation (in hours) will be calculated as the sum of all durations from first dose until trial termination per category and subject. Missing information on individual records will be imputed in the following way

- If start time is missing: impute with 0:00 .
- If end time is missing: impute with 23:59.
- If start day/month is missing: impute with first day (01) / month (Jan) if this falls within trial window, otherwise impute with day/month of first contact in the trial.
- If end day/month is missing: impute with last day (31) / month (Dec) if this falls within trial window, otherwise impute with day/month of trial termination.

In case of overlapping records, the duration will be calculated only once for the overlapping part of the records. .

**14.2.9 Duration of hospital/ICU stay:**

Defined as the time between hospital admission and discharge (in days)

- If start time is missing: impute with 0:00.
- In case end time is missing: impute with 18:00 .
- If start day/month is missing: impute with first day (01) / month (Jan) if this falls within trial window, otherwise impute with day/month of first contact in the trial.
- If end day/month is missing: impute with last day (31) / month (Dec) if this falls within trial window, otherwise impute with day/month of trial termination.

In case the subject is still hospitalized at the end of the trial, the trial termination date will be used.

#### **14.2.10 Duration of hospital stay for RSV**

The time between hospital admission and discharge (in days), similar to regular hospital stay but excluding prolongation due to SAE other than RSV worsening. SAE considered as RSV worsening are selected on SOC (“Respiratory, thoracic and mediastinal disorders” or “infections and infestations”) and PT (for infections and infestations only) by:

- Including any from: ‘bronchiolitis’, ‘pneumonia’, ‘bronchitis’, ‘RSV’
- Excluding ‘bacterial’

Imputation rules follow the rules for duration of hospital stay. Subject with a prolongation due to SAE other than RSV worsening will be censored at the SAE onset date.

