#### *Other Endpoints*

- Evolution over time in clinical symptoms (SpO2, feeding, respiratory rate, wheezing, cough, respiratory muscle retractions, and general appearance)
- Evolution over time in RDAI, RACS
- Length of hospital stay for RSV defined as time between admission and discharge
- Duration of supplemental oxygen therapy
- Initiation of invasive and non-invasive ventilation and duration of respiratory support
- Transfer to ICU and duration of ICU stay
- Parent(s)/Caregiver(s) assessment of the clinical condition of the subject
- Evolution of serum biomarker over time

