## 7.3 Other Efficacy Analyses

- Evolution over time in clinical symptoms will be evaluated. The body temperature and respiratory rate (actual values, change from baseline and percent change from baseline) will be summarized descriptively over time. Frequency tabulations will be provided to summarize the feeding, respiratory distress parameters (Wheezing (during inspiration/expiration), lung fields affected, crackles/crepitations, respiratory muscle retractorations (supravascular, intercostal and subcostal) , cough and general appearance of the subject over time. Respiratory rate and body temperature will also be presented graphically in mean  $\pm$  SE plots (excluding the in-hospital post-treatment timepoints).
- Respiratory Distress Assessment Instrument (RDAI) and Respiratory Change Score (RACS) will be calculated (see Section 14.2.3 and 14.2.4 for calculation method, respectively) . Actual values (RDAI, RACS) and changes from baseline (RDAI) will be summarized over time using descriptive statistics (both subitem and totals). RDAI, change from baseline in RDAI and RACS will also be presented graphically in mean  $\pm$  SE plots (excluding the in-hospital post-treatment timepoints). Similar to GSS, bar charts will be generated for RDAI to visualize contributing subitems.
- Length of hospital stay (in days – see section 14.2.9 for calculation method) defined as time between admission and discharge for the initial hospitalization will be summarized as descriptive statistics and using KM estimates. In case of missing discharge information the subject will be censored on date(time) of trial termination.
- The time between first study drug administration and discharge (in days) for the initial hospitalization will be summarized as descriptive statistics and using KM estimates. In case of missing discharge information the subject will be censored on date(time) of trial termination.

- Length of hospital stay for RSV: The time between hospital admission and discharge (in days) excluding prolongation due to SAE other than RSV worsening. Time will be summarized as descriptive statistics and using KM estimates. In case of missing discharge information the subject will be censored on date(time) of trial termination. If needed time will be imputed with 18u00 (see section 14.2.10 for calculation details).

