**Table 14.2.6.2: Hospitalisation – Length of hospital stay for RSV.**

Descriptive statistics of total length of hospital stay and Kaplan-Meier analysis. The output will include number of events, number of censored values, median, 25% percentile and 75% percentile of time to event with 95% CIs.

Population: mITT population.

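### SAP 14.2.10 censors the hospital stay for RSV at the onset of a stay-prolonging non-RSV SAE, drug-related or not, and SAP 13 does not declare this change from the protocol

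*SAP*

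**What the plan says.** Protocol 3.6.4, Other Endpoints: "Length of hospital stay for RSV defined as time between admission and discharge". No SAE is excluded.

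SAP 14.2.10 gives the same-named endpoint as "similar to regular hospital stay but excluding prolongation due to SAE other than RSV worsening", and carries it out as follows: "Subject with a prolongation due to SAE other than RSV worsening will be censored at the SAE onset date". SAP 4.3.3 repeats the exclusion.

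What counts as RSV worsening is set by coding: "SAE considered as RSV worsening are selected on SOC", with two classes admitted (respiratory, and infections), "and PT (for infections and infestations only) by" a search for four strings (bronchiolitis, pneumonia, bronchitis, RSV) that drops bacterial terms. The whole respiratory class is therefore RSV worsening, and only infection terms are filtered. Drug relatedness plays no part.

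For reporting, SAP 7.3 says "Time will be summarized as descriptive statistics and using KM estimates", and the shell of Table 14.2.6.2 reads "Descriptive statistics of total length of hospital stay and Kaplan-Meier analysis". Neither says how a censored stay enters the descriptive part.

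SAP 7.3 also has an all-cause stay, "defined as time between admission and discharge for the initial hospitalization will be summarized as descriptive statistics and using KM estimates" (Table 14.2.6.1), and a time from first dose to discharge (Table 14.2.6.3). Neither has SAE censoring. SAP 13 lists the Cox model, three added endpoints and the subgroup analyses, but not the new meaning of stay for RSV.

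**The concern.** There are five separate difficulties.

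1. The output that carries the protocol's endpoint name is no longer the protocol's endpoint, and the section meant to record such changes is silent.
2. Protocol 1.3.3 names hypersensitivity and allergic reactions as potential risks of a therapeutic protein. If such a reaction is serious, prolongs the stay and is coded outside the respiratory class, the extra days vanish from the arm in which the drug caused them.
3. The filter misses RSV illness. Lower respiratory tract infection, coded as an infection, contains none of the four strings. Dehydration or feeding failure falls outside both classes, although oral feeding is one of the two clinical response criteria and one of the three entry severity criteria.
4. The definition removes the prolongation, but the rule stops the clock at onset. The RSV days between SAE onset and the discharge that would have come anyway are lost too.
5. The censoring is triggered by an event that delays discharge, so it is informative for the time to actual discharge. Prolonged hospitalization is itself a seriousness criterion (Protocol 3.5.2). No rule says who decides that a prolongation was due to an SAE, or whether that is done blinded.

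At stake is a biased comparison of hospital stay between dose groups.

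**Working it through.** **No plan figure to reproduce.** The documents give no expected stay, no rate of prolonging SAEs and no effect size for this endpoint. The definitions were compared as set out above. The rest is frequency and illustration.

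**Step 1: how many infants?** Protocol 1.2.3 reports possibly related events in 3 subjects (8.6%) of the active group of the earlier infant study, so that group had 3 / 0.086 = 34.9, about 35 subjects. Four had SAEs: hypotonia with hyporesponsiveness (1), pneumonia (2), atelectasis (1). Taking pneumonia as an infection and atelectasis as respiratory, 1 of the 4 falls outside the SAP's list. The rate is 1/35 = 2.9%. Per arm of 45 that is 45/35 = 1.3 infants, and over 135 active subjects 135/35 = 3.9. Whether that SAE prolonged the stay is not stated. One event is weak evidence, so rates up to 20% are also shown.

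**Step 2: effect of the rule.** All inputs are assumed: lognormal stay with median 4 or 6 days and log-SD 0.5; an SAE adding 5 or 10 days; onset at 30% to 100% of the stay the child would otherwise have had; truncation at 28 days; 200,000 simulated stays per scenario. Selected results, in days:

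| Median stay, share affected, days added | Full stay: mean / median | Censored times used as values: mean / median | KM median | KM 28-day restricted mean | Mean had no SAE occurred |
|---|---|---|---|---|---|
| 4, 2.9%, +5 | 4.67 / 4.07 | 4.48 / 3.96 | 4.02 | 4.56 | 4.53 |
| 6, 2.9%, +10 | 7.09 / 6.11 | 6.73 / 5.94 | 6.04 | 6.85 | 6.80 |
| 6, 10%, +10 | 7.79 / 6.45 | 6.56 / 5.78 | 6.17 | 6.98 | 6.80 |
| 6, 20%, +10 | 8.79 / 7.05 | 6.33 / 5.56 | 6.35 | 7.20 | 6.80 |

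- At 2.9%, the KM median falls by 0.05 (4.07 − 4.02) to 0.07 (6.11 − 6.04). A descriptive mean that used censored times would fall by 0.19 (4.67 − 4.48) to 0.36 (7.09 − 6.73).
- Over all scenarios the KM median falls by 0.05 to 0.70 (7.05 − 6.35), and such a descriptive mean by 0.19 to 2.46 (8.79 − 6.33).
- In row 3 the descriptive mean of 6.56 lies below the 6.80 that the same children would have had with no SAE. The rule removes 6.80 − 6.56 = 0.24 day of ordinary stay on top of the prolongation.
- In row 3 the KM restricted mean (6.98) matches neither the full stay (7.79) nor the SAE-free stay (6.80). Once onset is tied to the child's own course, KM estimates neither quantity.

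**Step 3: can the arms change order?** Assume a median of 5 days, log-SD 0.45, onset uniform on days 1 to 4, and a mean of 5 days added. Compare an arm with 5% such SAEs to one with 10%:

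| | 5% | 10% |
|---|---|---|
| Full stay, mean | 5.79 | 6.03 |
| Full stay, median | 5.12 | 5.24 |
| Censored times averaged as stays | 5.38 | 5.22 |
| KM median | 5.02 | 5.03 |

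The order reverses only in the third row. KM shrinks a true difference in medians of 0.12 (5.24 − 5.12) to 0.01 (5.03 − 5.02) but does not reverse it. Even the third-row gap, 5.38 − 5.22 = 0.16 day, is small against sampling error. The SD of the assumed stay is 5·exp(0.45²/2)·√(exp(0.45²) − 1) = 5.53 × 0.474 = 2.62, so the standard error of a difference between arms of 45 is 2.62·√(2/45) = 0.55 day.

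**The case against.** The sponsor can fairly say that little hangs on this. It is one of twelve other endpoints in SAP 4.3.3, with no test, no subgroup analysis and no topline flag. The protocol's quantity is not lost: all-cause stay is admission to discharge without SAE censoring, and time from first dose to discharge gives a second uncensored view. A hypersensitivity SAE is not hidden either, because serious and treatment-related events have their own tables. Restoring the protocol definition under the RSV name would only duplicate Table 14.2.6.1. All of this stands, and it limits the size of the point.

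Three stronger readings are tempting, and the documents do not support them.

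- A reader might infer that any SAE off a narrow list cuts the stay short. The rule reaches only SAEs that prolong the stay, and the list is broad on the respiratory side. Bronchoconstriction coded to the respiratory class, for instance, keeps its full stay.
- A reader might infer that the arm with more complications will report the shorter stay. That requires averaging censored times as completed stays. The SAP leaves this open but does not prescribe it, and KM reads such a stay as longer than the censoring time.
- A reader might infer that the longest stays are reduced to a few days. The documents give no length of stay, so this rests on assumed figures.

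The objection does not answer the undeclared redefinition, the missing exemption for drug-related SAEs, the misclassified RSV terms, the loss of RSV days after onset, or the absence of a rule for deciding that an SAE caused the prolongation.

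**Conclusion.** The point holds as a defect of definition with a small expected numerical effect. Stay for RSV in the SAP differs from the protocol endpoint of that name, and SAP 13 does not say so. As written, the rule can remove drug-caused prolongation from the arm that produced it, treats some RSV illness as unrelated, and takes away more than the prolongation it says it excludes. These conclusions follow from the text, apart from how particular events would be coded.

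The size rests on assumptions. If 1 in 35 carries over, about one infant per arm is censored and the KM median moves by less than 0.1 day. At 10% to 20% the shift is a few tenths of a day, up to 0.7. A larger distortion, or a reversal between arms, needs censored times entered into descriptive means. That should be ruled out in words, but it is not what the SAP says will be done. No primary or key secondary conclusion is affected.

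**What to change.** 1. Name all-cause stay (Table 14.2.6.1), which is the protocol definition, as the hospital-stay result.
2. Give the SAE-excluding version its own name, such as stay excluding unrelated SAEs, and list it in SAP 13.
3. In that version, do not censor or exclude SAEs at least possibly related to study drug. The dichotomy in SAP 8.1.4 can be reused.
4. Replace the term search with classification by the sponsor's existing medical staff, done blinded and before unblinding. Count lower respiratory tract infection, and RSV-related feeding or dehydration events, as RSV illness. Record in the same review whether the SAE prolonged the stay.
5. Treat the remaining unrelated SAEs as a competing event and report the cumulative incidence of discharge, instead of censoring at onset.
6. Keep censored times out of descriptive means and medians, and report the number of affected infants by arm and SAE term.

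The cost is SAP wording, a short blinded review of what should be a handful of SAEs, and slightly more derivation work on one descriptive endpoint. No new data are needed.

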#### **14.2.11 Time between first study drug administration and discharge**

Defined as the time between first study drug administration and discharge (in days).

Imputation rules follow the rules for duration of hospital stay.

In case the subject is still hospitalized at the end of the trial, the trial termination date will be used.

#### **14.2.12 Time to child’s condition as before RSV onset**

Time to child’s condition as before RSV onset (in days) is defined as the time between first study drug administration and the first time the subject reaches the condition as before RSV onset as documented by the general health questionnaire. In case the subject does not reach the condition as before RSV, the time is censored at the last day with caregiver assessment equal to ‘No’.

### **14.3 Safety**

#### **14.3.1 Adverse Events**

##### **14.3.1.1 Handling of missing/partial date/time**

In case the adverse event (AE) start date(time) is incomplete, a conservative approach will be taken based on the available parts of the AE start date(time).

If the AE start time is missing and the AE start date is equal to or after the first date of study drug administration, then the AE is considered treatment emergent. If the day on which the AE started is missing and the month & year are the same or after the month & year of the start

of study drug administration or if the day and month on which the AE started are missing and the year is the same or after the year of the start of study drug administration, then the AE is considered treatment emergent (unless the AE end date is before the first study drug administration).

#### **14.3.1.2 Calculation of derived variables**

Following derived variables will be calculated:

AE duration

- = AE stop date – AE start date + 1 day (when both dates are completely known)
- = trial termination date – AE start date + 1 day (when the AE start date is fully known but the AE is not resolved at the end of the trial): in this case the duration will be presented as “>x days” in the listing rather than “x days”
- = missing (when the AE start date is incomplete or unknown, or when the AE has resolved but with an incomplete or unknown end date).

#### **14.3.2 Laboratory Evaluations**

##### **14.3.2.1 Handling of missing data: Differential blood cell counts**

In case of missing differential blood cell count, if either the absolute count or % is missing, the other one will be re-calculated on the available data if possible. Both values will be reported.

##### **14.3.2.2 Abnormal values**

Values will be scored as abnormally low (L), normal (N) or abnormally high (H). A value is classified as abnormally low when the value < lower limit of the normal range. A value is classified as abnormally high when the value > upper limit of the normal range. Laboratory parameters without quantitative values reported but indicated as NEGATIVE will be categorized as normal and values indicated as POSITIVE will be categorized as abnormal high. Values below the upper limit but without lower limit provided will be categorized as normal. Other tests without normal ranges will not be scored. An original value like “<X” where X equals the lower limit of the normal range will be classified as abnormally low (L). An original value like “>X” where X equals the upper limit of the normal range will be classified as abnormally high (H).

##### **14.3.2.3 Worst Case abnormalities**

Following categories will be used in the analysis

- H = abnormally high: at least one post-dose measurement is above the normal range, and there are no values below the normal range.
- L = abnormally low: at least one post-dose measurement is below the normal range, and there are no values above the normal range.

- H+L = abnormally high and low: at least one post-dose measurement is above the normal range, and at least one other post-dose measurement is below the normal range.
- N = normal: all post-dose measurements are within normal limits

#### 14.3.2.4 Handling of values below (or above) a threshold for descriptive statistics

For general safety labs values below (above) the detection limit will be imputed by the value of the detection limit itself, unless indicated otherwise. For virology results, values below the lower limit of quantification will be imputed by half of the value of the lower limit of quantification itself. For KL-6, values below the lower limit of quantification will be imputed by the value of the lower limit of quantification.

Listings will always present the original value. Example: if the database contains values like “<0.04”, then for the descriptive statistics the value of the detection limit (0.04) shall be used. A value like “>1000” will be imputed by “1000”.

## 16 INDEX OF TABLES

Tables and figures which will be part of the topline results are flagged with “(T)” in the titles.

### 16.1 General

#### Table 14.1.1.1: Subject disposition: Tabulation by analysis population

Tabulation of the number of subjects in each of the analysis populations.

Population: all screened population.

#### Table 14.1.1.2: Subject disposition: Tabulation by country and site

Tabulation of the number of subjects per country and site.

Population: ITT.

**Table 14.1.1.3: Subject disposition: First and last contact in the trial**

List the following 3 dates:

- Date of the first signature on study ICF or RSV test ICF
- Last visit date (all visits; including unscheduled visits)
- Last date of contact in the study with any subject.

Population: all screened population.

**Table 14.1.1.4: Screening failures and Treatment and Trial termination: Tabulation (T)**

Tabulation of:

number of screened, randomized and treated subjects and number of screening failures, together with primary reason for failure

trial and treatment completion/discontinuations and the reasons for discontinuation.

Population: all screened population.

**Table 14.1.1.5: Major Protocol deviations: Tabulation**

Tabulation of the protocol deviations per class.

Population: mITT.

**Table 14.1.1.6: Major Protocol deviations leading to exclusion from the per protocol population: Tabulation**

Tabulation of the protocol deviations leading to exclusion of the PP population per class.

Population: RSV infected.

**Table 14.1.2.1: Demographic data: Tabulation and descriptive statistics (T)**

Continuous parameters: descriptive statistics.

Categorical parameters: frequency tabulation.

Part 1: Modified intent-to-treat population.

Part 2: RSV infected population

Part 3: Per protocol population

**Table 14.1.2.2: Baseline disease characteristics: Tabulation and descriptive statistics (T)**

Continuous parameters: descriptive statistics.

Categorical parameters: frequency tabulation.

Part 1: Modified intent-to-treat population.

Part 2: RSV infected population

Part 3: Per protocol population

**Table 14.1.2.3: Baseline disease characteristics: Viral screening tests (T)**

Frequency tabulation per group of the results of the viral screening tests (refer to 19.4 for complete list)

Part 1: Modified intent-to-treat population.

Part 2: RSV infected population

Part 3: Per protocol population

**Table 14.1.2.4: Medical history: Tabulation by category**

Tabulation of medical history by category. Table entries are sorted alphabetically by category.

Population: mITT population.

**Table 14.1.2.5: Prior therapies by ATC 4 class and generic term**

Tabulation of the generic terms and ATC level 4 code of previous therapies.

Population: safety population.

**Table 14.1.2.6: Concomitant therapies by ATC 4 class and generic term**

Tabulation of the generic terms and ATC level 4 code of concomitant therapies.

Population: safety population.

**Table 14.1.2.7: Exposure to study medication: administration per day**

Tabulation of number of subjects with administration per day/timepoint. Includes frequency tabulation on compliance parameters:

Population: safety population.

**Table 14.1.2.8: Exposure to study medication: Compliance**

Descriptive statistics on treatment compliance

Population: safety population.

## 16.2 Efficacy

**Table 14.2.1.1: Primary Endpoint: Time to below quantification limit of RSV viral load (plaque assay) (T)**

Kaplan-Meier analysis, including a two-sided Log-rank test. The output will include number of events, number of censored values, median, 25% percentile and 75% percentile of time to event with 95% CIs and p-value of the log-rank test. Additionally the results of a Cox proportional hazards regression model with time to BQL as dependent variable, and treatment group, viral load at baseline and co-infected subject group as independent variables will be reported including Hazard ratio (95% CI) and p-value

Population: mITT population.

**Table 14.2.1.2: Sensitivity analysis - Time to below quantification limit of RSV viral load (plaque assay)-RSV Infected population (T)**

Kaplan-Meier analysis, including a two-sided Log-rank test. The output will include number of events, number of censored values, median, 25% percentile and 75% percentile of time to event with 95% CIs and p-value of the log-rank test. Additionally the results of a Cox proportional hazards regression model with time to BQL as dependent variable, and treatment group, viral load at baseline and co-infected subject group as independent variables will be reported including Hazard ratio (95% CI) and p-value

Population: RSV infected population.

**Table 14.2.1.3: Sensitivity analysis - Time to below quantification limit of RSV viral load (plaque assay)-Per Protocol analysis (T)**

Kaplan-Meier analysis, including a two-sided Log-rank test. The output will include number of events, number of censored values, median, 25% percentile and 75% percentile of time to event with 95% CIs and p-value of the log-rank test. Additionally the results of a Cox proportional hazards regression model with time to BQL as dependent variable, and treatment group, viral load at baseline and co-infected subject group as independent variables will be reported including Hazard ratio (95% CI) and p-value

Population: Per Protocol population.

